3.13.3. Primary Efficacy, Safety, and Immunogenicity Analysis

The primary analysis of efficacy, safety, and immunogenicity data occurred following the cutoff date of 25 September 2017, after all patients enrolled into Stage 3 completed at least 4 cycles of treatment with tagraxofusp, have experienced disease progression, or have withdrawn from the study. The primary analysis included efficacy, safety, PK, and immunogenicity analysis of Stage 3 data. In addition, supporting data from Stages 1 and 2 were analyzed at this time in support of the BLA.

3.13.4. Updated Reporting and Stage 4 Analysis

Following a data cutoff date of 13 March 2020 (database lock), updated reports are planned to support the ongoing efficacy and safety of Stages 1, 2, and 3 patients as well as to summarize the efficacy and safety of the lyophilized formulation of tagraxofusp, administered in Stage 4. A summary of efficacy, safety, PK, and immunogenicity analyses will be presented at this time.

The Updated Reporting and Stage 4 Analysis is described in this SAP.

4. STUDY ANALYSES

4.1. Patient Disposition

Patient disposition will be tabulated and include the number screened, the number treated in total, the number in each patient population for analysis, the number treated in each Stage of the study, the number receiving the frozen liquid and lyophilized drug formulation, the number on study at the time of data cutoff, the number who withdrew prior to completing the study and reason(s) for withdrawal. The summary will be presented by disease and line of therapy (first-line BPDCN, R/R BPDCN, AML) within Stage.

A data listing of study completion information, including the reason for premature study withdrawal, if applicable, will be presented.

4.2. Demographics and Baseline Characteristics

Demographics and baseline characteristics will be summarized and presented by disease and line of therapy (first-line BPDCN, R/R BPDCN, AML) within Stage. Age, height, and weight will be summarized using descriptive statistics (number of patients, mean, standard deviation, median, minimum, and maximum). The number and percentage of patients in each gender, ethnicity and race category will be presented.

Medical history and results from baseline screens such as for pregnancy, and smoking status will be tabulated. Primary disease history will be summarized including sites and extent of disease involvement, molecular markers, mutations, BPDCN baseline diagnosis (type of analysis, immunophenotype expression), and time since BPDCN diagnosis. Prior chemotherapy, prior immunotherapy, prior radiation therapy, and prior SCT will be summarized.

Demographic and baseline data for each patient will be provided in data listings.

4.3. Efficacy Evaluation

Data for all efficacy endpoints will be presented in by-patient listings. Efficacy summaries will be presented by stage of enrollment and line of therapy. Subgroup analyses will be reported for Stage 4 (and Stages 3 and 4 if pooled) according to whether patients were bridged to SCT posttreatment and not bridged to SCT post-treatment. Efficacy analyses of responses will also be summarized by baseline disease site.

4.3.1. Response Rate

Complete response rate will be presented as the number and percentage of patients who achieved CR (CR + CRc) after treatment with tagraxofusp.

Bone marrow CR (BMCR) rate will be measured by pooling data from patients who had either CR or PR according to the IWG response criteria, together with BMCR (reduction to $\leq 5\%$ BM blast cells), as a proportion of all patients with marrow disease ($>5\%$ BM blast cells) at baseline.

Objective response rate will be presented as the number and percentage of patients who achieve CR (CR + CRc), CRI, or PR after treatment.

For CR, BMCR, and ORR, 95% Clopper Exact CIs will be presented.

Permutation test results for Stage 3 and Stage 4 comparison will be reported as the observed results and relative percentile of the empirical null distribution for CR and ORR. Graphical plots may be presented.

4.3.3. Bridge to Stem Cell Transplant

The number and proportion of patients who receive SCT subsequent to achieving an investigator-determined outcome from tagraxofusp that is deemed by the investigator to enable a SCT, will be reported with 95% Clopper-Pearson Exact CIs. Summaries will be performed overall and by treatment outcome on tagraxofusp. Permutation test results for Stage 3 and Stage 4 comparison will be reported as the observed results and relative percentile of the empirical null distribution. Graphical plots may be presented.

4.3.4. Progression-Free Survival

Progression-free survival is defined as the time from the date of first infusion of tagraxofusp to the date of PD or death from any cause, whichever occurred first. For patients who receive SCT, PFS will include time to PD or death post-transplant. Patients who do not progress and are still alive at the time of analysis will be censored on the date of last treatment recorded prior to the analysis cut-off date. If patients start other anticancer therapies (with the exception of SCT), they will be censored at the latter of the date of last treatment with tagraxofusp or date of last disease assessment recorded that occurred prior to the start of the new therapy. The distribution for PFS will be estimated by Kaplan-Meier methodology and the 25th percentile, median, 75th percentile, number and percentage of events and censored observations, and appropriate CIs will be presented.

4.3.5. Overall Survival

Overall survival is defined as the time from the date of first infusion of tagraxofusp to the date of death from any cause. Patients still alive or lost to follow-up at the time of the analysis will be censored on the last date known to be alive prior to the analysis cut-off date, as determined by in- person visit or telephone contact. The overall distribution for OS will be estimated by Kaplan-Meier classical methodology in a similar manner to PFS.

4.3.6. Exploratory Endpoints

4.3.6.1. Time to Event Endpoints

Time to CR is defined as the time from initiation of treatment with tagraxofusp to CR (CR, or CRc, whichever is achieved first). Only patients who have achieved CR or CRc will be included in the analysis. Time to CR will be summarized using descriptive statistics.

Time to response is defined as the time from initiation of treatment with tagraxofusp to CR (CR + CRc), CRi, or PR, whichever occurs first. Only patients who achieve CR, CRc, CRi, or PR will be included in the analysis. The analysis of TTR will follow the same methods as described for TTTR.

Time to BMCR is defined as the time from initiation of treatment with tagraxofusp to BMCR, defined as the first evaluation of marrow blast cells $\leq 5\%$, for the patients who had evidence of BM disease ($> 5\%$ BM blast cells) at baseline. Only patients who have BM disease at baseline and achieve BMCR will be included in the summary. The analysis of time to BM response will follow the same methods as described for TTTR.

Time to progression is defined as the time from first treatment with study drug disease progression. Patients who do not progress or die prior to response will be censored on the date of last disease assessment recorded prior to the analysis cut-off date. The distribution for TTP will be estimated by Kaplan-Meier methodology and the 25th percentile, median, 75th percentile, number and percentage of events and censored observations, and appropriate CIs will be presented.

Relapse free survival (RFS) is defined as the time from CR (CR/CRc) to disease progression or death. For patients who receive SCT after CR/CRc, RFS will include time to disease relapse post-transplant. Patients who do not achieve CR or die prior to CR will not be included in the analysis. Patients who have responded and are alive at the time of analysis will be censored on the latter of the date of last treatment with tagraxofusp or date of last disease assessment

recorded prior to the analysis cut-off date. The distribution for RFS will be estimated by Kaplan-Meier methodology and the 25th percentile, median, 75th percentile, number and percentage of events and censored observations, and appropriate CIs will be presented.

4.3.6.2. Protocol-Specified Rate of Complete Response

The Study Protocol Amendment 9 (09 February 2017)-defined rate and duration of CR, inclusive of CR, CRc, and CRI will be summarized by disease and line of therapy (first-line BPDCN, R/R BPDCN, AML).

4.3.6.3. Additional Analyses

Sites and extent of disease involvement, as reported by the investigators, will be listed by Stage over time. For continuous disease measures Stages may be compared using ANOVA regression. Frequencies of categorical disease measures may be compared between Stages using chi-square tests of independence.

For a subset of efficacy parameters, additional supportive analyses may be performed based on the IRC-determined assessments of disease response over time. Efficacy parameters may include CR rate and ORR, and will be analyzed in a similar manner as was described in [Section 4.3.1](#) and [Section 4.3.2](#).

4.4. Safety Analyses

With the exception of Subgroup Analyses ([Section 3.9](#)), all safety tabulations will be presented by disease (first-line BPDCN, R/R BPDCN, AML) for all patients in the Safety Population by stage of enrollment (all doses included). All safety tabulations will be presented for first-line BPDCN patients in the Safety Population who were treated at 12 µg/kg/day by stage of enrollment and for those treated with lyophilized formulation of tagraxofusp.

4.4.1. Study Drug Exposure

Duration of study drug exposure will be calculated as the number of days and number of cycles patients were administered study drug.

$$\begin{aligned} & DDDDDDDDDDDDDDDDD DDoo SSDDDDuuuu DDDDDDDDD EEEEEEDDEEDDDDEE = \\ & (DDDDDDDEE DDoo llDDEEDD uuDDEEEE - DDDDDDEE DDoo ooDDDDEEDD \\ & uuDDEEEE) + 1 \end{aligned}$$

Duration in cycles of drug exposure will be defined the total number of cycles of study drug initiated while the patient is on study. Dose modifications, including frequency of dose interruptions and dose reductions will be summarized. Total dose administered will be summarized overall and by cycle.

Relative Dose Intensity will be computed using the following definition and summarized by disease and line of therapy by stage:

$$\begin{aligned} & SSDDSS(CCDDSSDDllDDDDDDDRREE AAAADDDDDll DDDDEEEE \\ & RREEAAEEDDRREEuu bbuu CCuuAAllEE) \end{aligned}$$

RREEI~~DDDDDR~~REE DDDDEEE I~~DDDD~~EEDDEEDDDuu (%) = 100 *

*SSDDSS(PPI~~DDDD~~DEEuu DDDDEEE DDDD bbEE
AAuuSSDDDDDEEDDEEuu bbuu CCuuAAlEE)*

Exposure to tagraxofusp will be presented in by-patient data listings.

4.4.2. Adverse Events

All AEs will be coded using the MedDRA coding system and displayed in tables and data listings using system organ class (SOC) and preferred term.

Analyses of AEs will be performed for those events that are considered treatment-emergent, where treatment-emergent is defined per protocol as any AE with onset after the first administration of tagraxofusp through 30 days after the last dose of tagraxofusp, or any event that was present at baseline but worsened in intensity or was subsequently considered drugrelated by the Investigator through 30 days after the last dose of tagraxofusp.

The number and percentage of patients with any treatment-emergent AE (TEAE), common AEs (defined as occurring in $\geq 10\%$ of the study sample), with any TEAE assessed by the Investigator as related to treatment, with TEAE occurring within 24 hours of infusion, with any TEAE with severity \geq Common Terminology Criteria for Adverse Events (CTCAE) Grade 3, with any serious adverse event (SAE), with any AE leading to discontinuation of study treatment, with any AE to dose reduction, and with any AE leading to dose interruption will be summarized by disease, line of therapy, dose and overall. In these tabulations, each patient will contribute only once (ie, the most related occurrence or the most intense occurrence) to each of the incidence rates in the descriptive analysis, regardless of the number of episodes.

Treatment-emergent AEs summarized by patient incidence rates are not tabulated by severity or relationship to study treatment; therefore, in such tabulations, a patient contributes only once to the count for a given AE SOC or preferred term. For tabulations that include classification by relationship to study treatment, AEs with missing relationship will be considered related to study drug. For tabulations that include classification by maximum severity grade, AEs with missing CTCAE severity will be included in a category for missing severity.

Incidence of TEAEs occurring within 24 hours of infusion will be summarized by SOC and preferred term.

Analysis of AEs over time will be conducted by presentation of AE incidence by cycle. For this analysis, incidence per cycle will be based on the onset of a particular preferred term event within the cycle, where onset is indicated by first or repeat occurrence or increase in severity of the event within that cycle. This analysis will be conducted for all AEs and for AEs of Grade ≥ 3 severity. For AEs of special interest, Kaplan-Meier analyses of time to first occurrence of Grade ≥ 2 severity will be conducted for FL BPDCN, R/R BPDCN, and AML patients.

AESI's will be determined using MedDRA version 19.0 standardized medical queries (SMQs), high-level terms, or preferred terms, as follows:

- Possible hypersensitivity events, based on the SMQ Hypersensitivity (broad search).

- Vascular capillary leak syndrome (CLS), based on the MedDRA SMQ [to be provided] in addition to preferred terms of hypoalbuminaemia, blood albumin decreased, and proteinuria.
- Visual acuity, based on the MedDRA preferred terms of visual acuity reduced, visual acuity reduced transiently, visual acuity tests abnormal.
- Post-transplantation veno-occlusive disease, based on the MedDRA preferred terms pulmonary veno-occlusive disease and veno-occlusive liver disease.
- Possible drug-induced liver injury events, based on the SMQ drug-related hepatic disorders (broad search).

Summary tables of AESIs produced will report AESI by preferred term, causality, severity grade, seriousness, and whether AESI led to discontinuation. These tabulations will be completed for all patients, by line of therapy for BPDCN patients, AML patients, and indication. AESIs will also be included in data listings.

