90 Minutes Post-Infusion		X		X		X		X
120 Minutes Post-Infusion		X		X		X		X
180 Minutes Post-Infusion		X		X		X		X
240 Minutes Post-Infusion		X		X		X		X

ECGs will be performed at 3 distinct time points (triplicates) within 5 minutes prior to each PK sample collection at the time points indicated.

10 Adverse Events and Safety Evaluation

The AE reporting period for a patient treated in the study begins with the initiation of SL-401 and is continuous through 30 days after the last SL-401 infusion. All AEs that occur in treated patients during the AE reporting period specified in the protocol must be reported to the Sponsor or designee, whether or not the event is considered related to SL-401. Any known untoward event that occurs beyond the AE reporting period that the Investigator assesses as related to SL-401 should also be reported as an AE.

All patients should be monitored per institutional guidelines for at least 4 hours following the administration of each infusion of SL-401. The Principal Investigator, who is a physician, or medical staff responsible for study conduct and safety evaluations, should be available during the administration SL-401 and follow-up to assess, treat, or report as necessary any AE or serious adverse event (SAE) that may occur.

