10.2 Period of Observation

Clinical signs and symptoms, and AEs (regardless of relationship to study treatment) will be collected continuously from the first day of SL-401 treatment to 30 days following the last infusion of SL-401. All SAEs and AEs judged to be related to study treatment will be collected throughout the follow-up period.

Conditions that the patient experienced prior to SL-401 treatment should be recorded in the patient medical history section of the eCRF. All the AEs should be followed-up until the symptoms dissipate or become stable even if AEs continue beyond the period of observation. AEs unresolved at the end of the observation period will be considered “ongoing” with an undetermined outcome; however, if after the period of observation completes but prior to the completion of the study, additional outcome information becomes available, it will be reported. The severity of the signs, symptoms, or AEs should be determined using the NCI CTCAE, Version 4.03. A complete CTCAE list can be downloaded at <http://evs.nci.nih.gov/ftp1/CTCAE/About.html>.

All clinically meaningful abnormal test results should be retested. Abnormal test results that are difficult to associate with the study drug should be followed until normalized or until the abnormality could be clearly attributed to another cause. Abnormal test results should not be reported as AEs unless they meet the criteria outlined in [Section 10.1.1](#).

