10.5 Documentation and Reporting of Adverse Events by Investigator

The Investigator is to report all directly observed AEs as well as those spontaneously reported by the patient using concise medical terminology. In addition, each patient will be questioned about AEs at each clinic visit following initiation of treatment. The question asked will be "Since your last clinic visit have you had any health problems?" or a similar non-leading question to assess health status.

The AE reporting period for this study begins upon initiation of SL-401 treatment and ends 30 days after the last infusion of SL-401. All AEs are to be reported on the AE eCRFs.

All AEs that occur in study patients during the AE reporting period specified in the protocol must be reported to the Sponsor or designee, whether or not the event is considered study treatment-related. In addition, any untoward event that occurs beyond the AE reporting period that the Investigator assesses as related to the investigational product should also be reported as an AE.

Each AE is to be classified by the Investigator as serious or non-serious. This classification of the gravity of the event determines the reporting procedures to be followed. If a SAE occurs, reporting will follow local and international regulations, as appropriate.

For any event that meets one of the SAE criteria, the Investigator [REDACTED] Safety **within 24 hours** of the knowledge of the occurrence. To report the SAE, the SAE form is to be completed electronically in the electronic data capture (EDC) system for the study. When

the form is completed, [REDACTED] personnel will be notified electronically and will retrieve the form. If the event meets serious criteria and it is not possible to access the internet, an email to should be sent to [REDACTED] or a call made to the [REDACTED]

[REDACTED] within 24 hours of awareness. When the EDC system becomes available, the SAE information must be entered within 24 hours of the system becoming available.

[REDACTED]

Each SAE should be followed until resolution, or until such time as the Investigator determines its cause or determines that, it has become stable.

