12.5 Analyses of Safety Data

Safety assessments include DLTs, AEs, SAEs, physical examinations, vital sign measurements, ECGs, clinical laboratory evaluations, and reasons for treatment discontinuation due to toxicity. Safety data analysis will be performed primarily on the pool of first-line BPDCN patients treated with the 12 µg/kg/day dose level, with additional summaries across all BPDCN patients, patients with R/R disease and the pool of all BPDCN patients. Separate safety tabulations will be produced for patients with AML, patients who are treated with the lyophilized formulation of SL-401, and an overall pool of all enrolled patients.

Treatment-emergent AEs through 30 days after last SL-401 infusion will be summarized by MedDRA™ Version 13.1 (or higher) System Organ Class and preferred term. The incidences and percentages of patients experiencing each AE preferred term will be summarized with descriptive statistics. AEs will also be summarized by National Cancer Institute Common Terminology Criteria for Adverse Events (NCI-CTCAE), Version 4.03 (or higher) grade and by causality (relationship to study treatment). Dose-limiting toxicities, \geq Grade 3 AEs, SAEs, and AEs resulting in dose modification or treatment discontinuation will also be summarized by preferred term.

Laboratory results will be classified according to NCI-CTCAE, Version 4.03. Laboratory results not corresponding to an NCI-CTCAE term will not be graded. Incidences of laboratory abnormalities will be summarized with descriptive statistics.

Vital signs, physical examination results, and ECGs will be summarized with descriptive statistics.

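### The related-AE and Grade ≥3 summaries stop 30 days after the last dose, although the protocol requires drug-related events to be reported beyond that point

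*SAP*

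**What the plan says.** **Collection.** Protocol section 10.5 sets the basic period: "The AE reporting period for this study begins upon initiation of SL-401 treatment and ends 30 days after the last infusion of SL-401". It then adds a rule for later AEs: "any untoward event that occurs beyond the AE reporting period that the Investigator assesses as related to the investigational product should also be reported". The opening text of section 10 carries the same extension ("Any known untoward event that occurs beyond the AE reporting period that the Investigator assesses as related to SL-401 should also be reported"), as does the synopsis. Section 10.2 is broader in wording: "All SAEs and AEs judged to be related to study treatment will be collected throughout the follow-up period".

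**Analysis.** SAP section 4.4.2 states that "Analyses of AEs will be performed for those events that are considered treatment-emergent". The first limb of its definition is "any AE with onset after the first administration of tagraxofusp through 30 days after the last dose of tagraxofusp". The second limb covers conditions present at baseline that worsen or come to be regarded as drug-related, and it ends at the same 30 days. Protocol section 12.5 sets the same limit: "Treatment-emergent AEs through 30 days after last SL-401 infusion will be summarized".

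Within the SAP's list of summary rows, the treatment-related row and the Grade ≥3 row are both named as TEAE rows. Other rows in the same sentence drop that label: "with any serious adverse event (SAE), with any AE leading to discontinuation of study treatment". SAP section 3.11 places everything recorded on the eCRF in listings.

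**The concern.** A table of drug-related adverse events is normally read as the count of events that investigators attributed to the drug. Under this plan it is the count of those that began by day 30 after the last dose. An event with later onset, attributed to tagraxofusp and reported as the protocol demands, has no summary table planned for it.

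The rule also sits oddly with the SAP's own cautious conventions. An AE with no recorded relationship is counted as related (section 4.4.2), and an AE with no onset date is placed on the first day of treatment (section 3.11). Unknown causality and unknown timing are therefore resolved towards counting the event, while an affirmed causal link is set aside if onset is on day 31. What is at stake is possible understatement of drug-related harm in the updated report, which covers all stages and the lyophilized formulation.

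**Working it through.** There is no planned figure to reproduce, so the check sets the collection rules beside the analysis rules.

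| Type of event, onset after day 30 | Must it be reported? | Is it tabulated? |
|---|---|---|
| Related AE | Yes: protocol synopsis, 10, 10.2 and 10.5 agree | No in the related row, which is TEAE-only |
| Related AE, Grade ≥3 | Yes, same sections | No in the Grade ≥3 row, which is TEAE-only |
| Related SAE or AESI | Yes, same sections | Unclear: these outputs repeat no window, but the opening sentence of SAP 4.4.2 appears to govern them |
| Unrelated SAE | Unsettled: 10.2 can be read either way; 10 and 10.5 extend related events only | Unclear, as above |
| Unrelated, non-serious AE | No | No, which is consistent |

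The first two rows need no inference: reporting is required, and the plan's own wording excludes the event from the table.

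**How much observation lies outside the window.** SAP section 1.1 gives 7 January 2019 as the end of Stage 4 enrolment, and section 3.13.4 gives 13 March 2020 as the cut-off. Assume that a patient first infused on that last date received one cycle of five consecutive daily infusions and stayed alive and in follow-up. The last infusion is on 11 January 2019 and the window closes on 10 February 2019. From there to the cut-off is 365 days (to 10 February 2020) + 32 days (19 to the end of February, 13 in March) = 397 days. Further cycles shorten this interval and earlier enrolment lengthens it.

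**What one event would do to a table.** Treated BPDCN patients number about 32 (interim analysis set, SAP 3.13.1) + 13 (Stage 3, SAP 3.1, taking all as treated) + 42 (Stage 4, SAP 1.1) = 87. One additional patient in a row changes its incidence by:

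- all treated BPDCN: 1/87 = 1.1 percentage points
- Stage 4 first-line, 37 treated (SAP 3.1): 1/37 = 2.7 points
- Stage 3 first-line, 13: 1/13 = 7.7 points

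**Where the effect would fall.** Each patient contributes once per row. Protocol section 3.7.2 reports treatment-related transaminase elevation in 54% of the 26 BPDCN patients at the July 2016 safety cut, so at least that share was already in the any-related row. A late event would therefore tend to alter preferred-term rows and worst-grade counts more than the headline row.

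**The case against.** The strongest reply is that a fixed 30-day window backed by full listings is a common choice, and that the SAP only carries out protocol section 12.5. This stands in part. The point is not a conflict between protocol and SAP: the mismatch already lies within the protocol, between sections 10, 10.2 and 10.5 on one side and 12.5 on the other. Collecting events for safety reporting over a longer period than is tabulated is not a contradiction in itself. It does not answer the narrower point that a related-AE table omits events recorded as related.

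A reader might infer more than the documents support:

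- **That all AE outputs are cut at day 30.** Only the opening sentence of SAP 4.4.2 suggests this. The SAE, discontinuation and dose-modification rows, the AESI tables, the capillary leak algorithm (8.3) and the counts by antibody status (4.5) state no window. They are ambiguous, not demonstrably truncated.
- **That late SAEs of any cause are collected and then lost.** In protocol 10.2 the qualifier about relatedness may apply to SAEs as well as AEs. Section 9.6 runs AE and SAE monitoring to 30 days, and the survival column of Table 8 marks none.
- **That late events disappear.** They remain in listings, and late deaths count in overall survival (SAP 4.3.5), though without attribution.
- **That a known late toxicity is being hidden.** Protocol section 3.8 describes visual loss with a different product as persistent, not as late in onset, and attributes it to that product's IL-2 component. No section describes late antibody-mediated reactions. The only late events specifically followed are veno-occlusive disease and engraftment problems after transplant (9.7, 10.1.1).

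It is also fair that reporting after day 30 relies less on scheduled questioning, so late and early rates are not of equal quality. That argues for showing them apart, not for leaving them out.

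**Conclusion.** The concern holds in a limited form. Investigator-attributed AEs with onset more than 30 days after the last dose must be reported, yet they are excluded by wording from the related and Grade ≥3 rows and have no other planned summary. The related-AE tables could therefore understate drug-related harm. For the SAE and AESI tables the finding is only that the window is unstated and should be settled.

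The number of affected patients cannot be estimated, since the documents give neither a count nor a rate of events after day 30; it may be zero. The per-patient effects above show scale only, and assume that the patient is not already counted in the row concerned. The conclusion rests on reading the TEAE label in SAP 4.4.2 as meaning the definition given there.

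**What to change.** 1. In SAP 4.4.2, and to match in protocol 12.5 and the synopsis, keep the 30-day window for all-cause TEAEs. Extend the treatment-emergent definition to include any AE that the investigator assesses as related to tagraxofusp, with onset at any time after first dose, so that these events enter the related, Grade ≥3, SAE and AESI tabulations.
2. State in the SAP that the SAE and AESI tables use this definition.
3. Show related events with onset after day 30 on a separate line, with a note that collection after day 30 is less systematic. Readers can then still recover the 30-day figures.
4. Say whether the rule that treats a missing relationship as related applies after day 30. Limiting the extension to events with a recorded attribution avoids bringing in late events that nobody has assessed.
5. Do not tabulate late unrelated SAEs unless protocol 10.2 is first reconciled with sections 10 and 10.5 and Table 8 on whether they are collected at all.

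The cost is revised wording and one derivation flag, with no new data collection for related events, since reporting of them is already required. The downside is that related-event rates may rise slightly.
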